1. PURPOSE OF THE STUDY

a. Brief Summary

Pain catastrophizing is a psychological response to pain that serves to make pain worse. In order to reduce suffering in people with chronic pain, it is important to treat pain catastrophizing. The purpose of the study is to test a single-session pain education class for treating pain catastrophizing in people with chronic pain on long-term opioid therapy. Class participants learn skills and develop a personalized plan to use the skills every day. The study will follow participants for 3 months by administering 5 follow-up surveys at 2 weeks and 1 month, 2 months, and 3 months post-treatment to determine whether the class confers long-term benefits across various aspects of health.

b. Objectives

The study will provide important information regarding the effectiveness of the pain education class and how well it reduces pain catastrophizing in patients on long-term opioid therapy for chronic pain. The information learned in this study will allow us to determine how reductions in pain catastrophizing may impact related health factors, such as pain, sleep, function, depression, and anxiety.

c. Rationale for Research in Humans

This research necessitates human participants because there is no equivalent animal model or non-human model to answer the study questions. The "Virtual Empowered Relief" (vER) class is designed for human participants only.

2. STUDY PROCEDURES

a. Procedures

I. Recruitment: Participants with chronic pain and opioid use disorder will be recruited by posting a flyer at methadone or buprenorphine clinics. Potential participants will be screened for interest and eligibility via the attached phone script. Participants will be informed that participation in the study is optional and not required as part of their care at methadone or buprenorphine clinics. They will also be informed that their information will not be shared with medical providers and staff at methadone or buprenorphine

clinics. During or after this call, all eligible participants will be invited to participate in the 2-hour Virtual Empowered Relief (vER) class.

Researchers at RTI International will be involved in recruiting study sites, check-in with each study site for posting a flyer, and resolve any recruitment issues at each site-contact. However, researchers at RTI will not have a direct contact with patients. Researchers at RTI may also analyze de-identified data and write a paper together.

II. Pre-Class Procedures: All interested and eligible participants will receive study information and informed consent will be obtained over the phone from each eligible participant prior to attending the vER class. Informed consent will be obtained on the phone with a research coordinator. All participants will have the informed consent presented to them through REDCap, emailed, or mailed to them.

Participants will complete the questionnaire using a secure, HIPAA-compliant, online system (via REDCap) or phone. Additionally, the questionnaire may be administered in hard copy form.

III. Intervention Pain Education Class "Virtual Empowered Relief" The participants will attend the class offered by pain psychologists at Stanford Pain Management Center or the Stanford Pain Relief Innovations Lab. This class will be held online via Zoom. The class will NOT be recorded. Zoom video function will be disabled so participants will NOT see other participants' faces. Participants will also be recommended to display only their first name. Class participants will learn skills and develop a personalized plan to use the skills every day. At the end of class, participants will be given a survey about the class. Treatment participants will receive a relaxation audio file via email or a CD/USB post-class via mail. We aim to give all patients rapid access to low-risk care that empowers them to self-manage their pain and reduce reliance on opioids. If participants cannot download the app, they will receive an audio file of the relaxation resource.

IV. Post-Class follow-up: Participants will be followed for approximately 3 months after completing the class. Participants will be asked to complete questionnaires at 2 weeks and 1, 2, and 3 months after the class. All participants will be provided a link to an online secure system (REDCap), paper, or phone to complete follow-up questionnaires.

All questionnaires to be administered by the research staff are attached under section 16 of the protocol.

Time line for questionnaire administration is as follows:

BEFORE CLASS:

- Demographics
- Treatment expectation
- Medication Use
- PROMIS clinical questions
- Non-PROMIS clinical questions

IMMEDIATELY AFTER CLASS:

- Post-class questionnaire

WEEKS 2 and MONTH 1, 2, and 3 POST-CLASS:

- Medication Use
- PROMIS clinical questions
- Non-PROMIS clinical questions
- Global Impression of Change
- Treatment change and adverse events

Participants may also be mailed a thank you note.

b. Procedure Risks

All members of the study team have been trained to conduct the research procedures in the safest manner possible. There are no known risks to completing the questionnaires or undergoing the vER class. Participants will be informed that they have the right to refuse to answer questions and they can withdraw from the study at any time. All the responses will not be shared with their medical providers and staff at their methadone or buprenorphine clinics.

c. Use of Deception in the Study

No deception will be used.

d. Use of Audio and Video Recordings

The class will NOT be recorded.

e. Alternative Procedures or Courses of Treatment

No standard treatment is being withheld. Participants are encouraged to continue with their current course of treatment for their pain under the care of their regular physician. Participant's alternative is to not participate.

f. Will it be possible to continue the more (most) appropriate therapy for the participant(s) after the conclusion of the study?

Participants are free to pursue the treatment of their choice at any time during and/or after the study

g. Study Endpoint(s)

Each participant will meet the study endpoint once he/she completes the last set of questionnaires at the final time point. The study will end once the target enrollment is reached.

3. BACKGROUND

a. Past Experimental and/or Clinical Findings

At Stanford Pain Management Center, we have routinely delivered the Empowered Relief class as pain psychology treatment and have received very high indices of satisfaction from class participants. Our previous NIH-funded study on patients with chronic low back pain has also shown reductions of pain, pain catastrophizing, and pain interference and increase in pain self-efficacy after taking the class. However, we do not know if vER is effective in patients with opioid use disorder and chronic pain. The current study will allow us to understand whether vER is effective in this patient population who usually has a limited access to pain psychology services. Based on the findings from the current study, we plan to apply for a NIH funding and do a large scale study.

Darnall et al., Comparison of a Single session Pain Management Skills intervention to a Single session Health Education Intervention to Eight sessions of Cognitive Behavioral Therapy in Patients with Chronic Low Back Pain: A Randomized Clinical Trial (Submitted to JAMA open)

b. Findings from Past Animal Experiments

NA

4. PARTICIPANT POPULATION

a. Planned Enrollment

i-iii) A total of up to 100 participants with chronic pain are expected to enroll.

b. Age, Gender, and Ethnic Background

Men and women, ages 18 and older of any race or ethnicity will be recruited.

c. Vulnerable Populations

NA

d. Rationale for Exclusion of Certain Populations

The pain catastrophizing protocols (Taub et al, 2016, Roditi et al, 2009) have been validated only for adults with chronic pain. This study will be the first to use this protocol

in patients taking opioid pain medications for chronic pain management. If this study finds no safety concerns in adult patients with chronic pain and chronic opioid therapy, a future study can include children.

e. Stanford Populations

All participants will be recruited at methadone and buprenorphine clinics in the US. Laboratory personnel and employees at Stanford will not be recruited for this study.

f. Healthy Volunteers

Healthy volunteers are not being recruited for this study

g. Recruitment Details

We will recruit patients from the methadone or buprenorphine clinics via a flyer (attached). Participants with chronic pain and opioid use disorder will be identified by a prescreening survey by a research staff at Stanford. We will also recruit patients from the Stanford Pain Clinic using the Stanford Pain Registry (<https://choir.stanford.edu/>). We will partner with the Research Participant Engagement Program (RPEP) team for Honest Broker outreach. Potential participants are identified via STARR and invited by RPEP team (honest broker) on behalf of study team. See Section 16 for Honest Broker study invitation letters. We will be using Postal Mail Honest Broker outreach. For Postal Mail, study team may support the process by sticking pre-printed address labels (created by RPEP, the honest broker) on the envelopes.

h. Eligibility Criteria

i. Inclusion Criteria

- 1) Age 18+
- 2) Chronic pain at least 3 month
- 3) Taking Methadone or buprenorphine

ii. Exclusion Criteria

- 1) Cognitive impairment
- 2) Pregnant
- 3) non-English speaking.

i. Screening Procedures

Contact information of potential participants will be collected from the Stanford Pain Clinic or via REDCap survey linked to the study website. Potential participants will be screened using the attached phone script (section 13) to determine eligibility prior to consent. We are obtaining a limited waiver of authorization to collect eligibility information in the phone screen as well as to access the patient's Medical Record and Clinic Registry (clinical questionnaire database) to assess eligibility.

j. Participation in Multiple Protocols

Participants will be asked whether they are enrolled in any other research studies. If another study's procedures interferes with our own or places the subject at increased risk, he/she will not be enrolled in our study.

k. Payments to Participants

Participants will be compensated with Amazon gift card for completing assessments at prescreening (\$10), baseline and post-intervention (\$20 & \$25), 2-week (\$20), 1-month (\$30), 2-month (\$20), and 3-month (\$20) after the class (\$145 total). Participants will be compensated with \$20 gift card for completion of optional lifetime OUD survey.

l. Costs to Participants

No costs will be charged to the participant.

m. Planned Duration of the Study

We estimate the study to take less than 1 year to complete.

- i) 1-3 months for recruitment and screening of participants
- ii) approximately 3 months of active participation, including 2.5 hours for the class, 15-20 minutes for completing each round of questionnaires, and a 15-30 minutes post class phone call by a Stanford Research Coordinator.
- iii) 3 months of analysis.

5. RISKS

a. Potential Risks

- i. Investigational devices

NA

- ii. Investigational drugs

NA

- iii. Commercially available drugs, biologics, reagents or chemicals

NA

- iv. Procedures

NA.

- v. Radioisotopes/radiation-producing machines

NA

- vi. Physical well-being

NA

vii. Psychological well-being

viii. Economic well-being

NA

ix. Social well-being

There is the risk that PHI will be accidentally be disclosed to people outside of the study staff.

x. Overall evaluation of risk

Minimum

b. International Research Risk Procedures

NA

c. Procedures to Minimize Risk

Risks of discomfort due to the questionnaires will be minimized by allowing the participant to refuse to answer particular questions.

All participant information will be stored in a locked cabinet and on an encrypted, password-protected computer.

Patients exhibiting signs of depression may be encouraged to speak to their medical providers at methadone or buprenorphine clinic.

d. Study Conclusion

The experiment will terminate when all participants have completed participation. If an individual participant chooses to withdraw, or the researcher determines it is unsafe or scientifically invalid for him/her to continue, his/her participation will end. We do not anticipate the study will directly result in adverse effects to the participants. However, we will encourage them to speak to their medical provider at methadone or buprenorphine clinic for any necessary medical intervention in the event of an adverse event.

e. Data Safety Monitoring Plan (DSMC)

i. Data and/or events subject to review

Self-reported adverse events were collected at each data point (monthly) for 3 months (the study endpoint). Adverse events were reviewed as soon as participants reported any events on the REDCap, which sent automatic email notification to [name], PI.

ii. Person(s) responsible for Data and Safety Monitoring

[name] [name]

iii. Frequency of DSMB meetings

N/A

- iv. Specific triggers or stopping rules
Any SAEs that are probably or possibly related to this study
- v. DSMB Reporting
No DSMB
- vi. Will the Protocol Director be the only monitoring entity? (Y/N)
Y
- vii. Will a board, committee, or safety monitor be responsible for study monitoring? (Y/N)
N

f. Risks to Special Populations

NA

6. BENEFITS

Participants may or may not experience benefits from the "Virtual Empowered Relief" (vER) class. The vER class is designed to help patients learn new skills to better cope with chronic pain. Knowledge gained from this study may inform future research studies and clinical treatments aimed at reducing catastrophizing in patients with opioid use disorder and chronic pain. Furthermore, the patient may also benefit from lowering opioid dose.

7. PRIVACY AND CONFIDENTIALITY

All participant information and specimens are handled in compliance with the Health Insurance Portability and Accountability Act (HIPAA) and privacy policies of Stanford University, Stanford Health Care, and Stanford Children's Health.

Virtual Empowered Relief for People With Chronic Pain Who Take Methadone or Buprenorphine

Statistical Analysis Plan

NCT05057988

June 6, 2024

Statistical Analysis Plan

Primary Outcome Analysis to Determine Feasibility

To determine the feasibility of a future RCT, we will evaluate the following criteria.

1. At least 75% of enrolled participants will attend the web-based ER class.
2. Demographic data (sex, age, race or ethnicity, education, income) will be compared between those who drop out and complete the study at the primary end point.
3. The mean scores of the 3 primary feasibility outcome measures will meet or exceed an 80% threshold of acceptability (8 or higher on a 0-10 scale).
4. The qualitative interview data will be analyzed to evaluate perceived feasibility and to identify areas for improvement in the study design for a future, large-scale RCT.

Secondary and Tertiary Outcome Analysis to Examine the Preliminary Efficacy

To test the secondary and tertiary hypotheses, repeated-measures ANOVAs will be conducted to examine whether the secondary and tertiary outcomes will be significantly changed over time. False discovery rate adjustments will be used to control for type 1 error for the multiple comparisons. If the ANOVA results reveal significant change in the outcomes over time, post hoc analyses will be conducted to examine whether the secondary and tertiary outcomes will be improved by 1 month (primary end point) or 3 months (secondary end point) after the web-based ER class.

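### The repeated-measures ANOVA that decides whether the 1-month and 3-month tests are run has no stated occasions or missing-survey rule; a mixed model on all surveys avoids a possible loss

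*SAP*

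**What the plan says.** The SAP's section on secondary and tertiary outcomes has three sentences. The first names the method: "repeated-measures ANOVAs will be conducted to examine whether the secondary and tertiary outcomes will be significantly changed over time". The second covers multiplicity: "False discovery rate adjustments will be used to control for type 1 error for the multiple comparisons". The third makes the time-point tests conditional: "If the ANOVA results reveal significant change in the outcomes over time, post hoc analyses will be conducted". The time points tested there are 1 month, labelled the primary end point, and 3 months, the secondary one.

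The occasions have to be looked for in the protocol. Section 2.a.IV says: "Participants will be asked to complete questionnaires at 2 weeks and 1, 2, and 3 months after the class". With the pre-class set, that makes up to five occasions. (The Brief Summary in section 1.a counts five follow-up surveys but lists four times.) Neither document links this schedule to the ANOVA, gives a rule for missed surveys, or names the data for the post hoc tests.

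Both documents foresee incomplete data. Under SAP feasibility criterion 2, demographics "will be compared between those who drop out and complete the study at the primary end point". Protocol section 2.b tells participants that "they have the right to refuse to answer questions and they can withdraw from the study at any time".

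On numbers, protocol section 4.a says: "A total of up to 100 participants with chronic pain are expected to enroll". SAP criterion 1 reads: "At least 75% of enrolled participants will attend the web-based ER class". That is 75 of 100.

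**The concern.** A classical repeated-measures ANOVA uses only participants with every occasion present. Run on all five occasions, it discards someone who answered at baseline and 1 month but missed, say, the 2-month survey. Because the ANOVA comes first, this reaches the primary end point in three ways:

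- A real change may fail the overall test, and its 1-month test is then never run.
- If the post hoc tests use the same rows, the 1-month estimate is less precise than the data allow.
- If people leave according to how they scored earlier, complete rows are a selected group and the estimate is biased.

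Criterion 2 does not deal with this. It compares demographics only, so it would not show dropout related to the outcome. Because the occasions and data set are unstated, they could also be chosen after the data are seen.

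**Working it through.** The SAP gives no power, variance or dropout figure for these outcomes, so there is no figure of the plan's own to reproduce.

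**Assumptions.** SD 1 at each occasion. Correlation is constant at 0.6 or 0.8^(months apart). Baseline is always present. A proportion p of 5%, 10% or 20% is missing at 1 month. Two patterns are used:

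- Dropout (monotone, constant rate h per survey): (1-h)^2 = 1-p at 1 month, so (1-h)^4 = (1-p)^2 are complete.
- Independent misses: (1-p)^4 are complete.

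**1-month responders dropped by five-occasion complete rows.** Under dropout, 1 - (1-p)^2/(1-p) = p. Under independent misses, 1 - (1-p)^3.

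**Variance of the change c'μ.** Complete rows give c'Σc/(n × proportion complete). The likelihood analysis gives c'[Σ over patterns of (pattern probability × inverse covariance of the observed occasions)]^-1 c / n. Example, p = 20%, dropout, correlation 0.6: complete rows 0.8/0.64 = 1.25; likelihood 0.948; ratio 1.32.

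| Pattern, p | Complete | 1-month responders dropped | 1-month ratio, five occasions | 1-month ratio, baseline/1/3 months | 1-month ratio, available pairs | 3-month ratio, five occasions |
|---|---|---|---|---|---|---|
| Dropout 5% | 0.90 | 5% | 1.07 | 1.07 | 1.01-1.02 | 1.03-1.04 |
| Dropout 10% | 0.81 | 10% | 1.14-1.15 | 1.14-1.15 | 1.03 | 1.07-1.08 |
| Dropout 20% | 0.64 | 20% | 1.32-1.33 | 1.32-1.33 | 1.05-1.07 | 1.13-1.17 |
| Independent 5% | 0.81 | 14% | 1.19-1.20 | 1.07-1.09 | 1.02-1.03 | 1.19-1.20 |
| Independent 10% | 0.66 | 27% | 1.43-1.46 | 1.16-1.18 | 1.04-1.06 | 1.43-1.46 |
| Independent 20% | 0.41 | 49% | 2.11-2.21 | 1.35-1.41 | 1.08-1.13 | 2.11-2.21 |

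A ratio of 1.33 widens the confidence interval by √1.33 = 1.15, that is 15%. A ratio of 1.07 widens it by 3%.

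**Power of the overall time test.** Take means 0, -0.20, -0.30, -0.30, -0.30 SD, correlation 0.6 and an unadjusted 5% level. The noncentrality is n × Σ(μj - mean)^2/(1-0.6) = n × 0.068/0.4 = 0.17n. With no missing data and N=100 it is 17.0 and power is about 92-93%. Under dropout at N=100 (noncentral F, large-sample approximation):

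- 5% missing: 89% for the five-occasion ANOVA, 90% for the mixed model.
- 10%: 85% and 88%.
- 20%: 75% and 84%.

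At N=75 the 10% and 20% figures are 72% against 75%, and 60% against 69%. With independent misses at N=100, simulation gives 75% against 91% (10%) and 49% against 89% (20%).

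**Bias.** A simulation used n=75, 400 runs, correlation 0.6 and a true change of -0.30 SD. Dropout started at the 1-month survey, and its log-odds rose by 1.0 per SD of worse preceding score. At dropout rates of 5%, 10% and 20% per survey for an average baseline score, the 1-month change from complete rows averaged -0.328, -0.332 and -0.355. The likelihood analysis gave -0.309, -0.303 and -0.295. At 3 months the two agreed (-0.291 and -0.294 at 20%).

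**The case against.** The strongest reply is that the loss is small under the pattern the plan itself describes. Criterion 2 speaks of people who drop out, and under dropout the 1-month variance ratio stays at or below 1.33, with little to gain at 3 months. At 10% dropout and N=100, an ANOVA on baseline, 1 and 3 months has the same power as the mixed model (88%). Retention is also supported: the protocol pays for each survey (section 4.k) and allows completion online, on paper or by phone (sections 2.a.II and 2.a.IV). All of this stands, and it limits the size of the point.

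A reader might infer more than the documents support:

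- That the SAP commits to five occasions and to deleting incomplete participants. It leaves both open.
- That half of the 1-month responders will be lost, or that power falls to 49%. Both need 20% missed independently at every survey and a five-occasion analysis.
- That the feasibility conclusions are at risk. The four feasibility criteria do not use the ANOVA.
- That a mixed model cures dropout bias. It does so only when missingness depends on observed data, and it cannot separate the class effect from natural course in a single-group study.

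What survives is that the overall test decides whether the primary end point is tested, its data are undefined, and a better method costs little.

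**Conclusion.** The point holds as a cheap improvement to the secondary and tertiary analysis. The three omissions are plain in the SAP, and the conditional step makes them matter at 1 month. The size rests on assumed missingness of 5-20% and assumed correlations. If people mainly drop out, the cost at 1 month is modest (variance 1.07-1.33 times) and at 3 months small (1.03-1.17). If they miss single surveys, the 1-month cost can reach about 2.2 times. Power for the overall test falls correspondingly: at N=100 and 20% dropout, 75% against 84%; at 5% dropout the difference is about one point. Bias arises only if leaving depends on scores. Complete rows then overstate improvement if those doing worse leave, and understate it if those doing better leave.

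**What to change.** Replace the SAP paragraph with text such as:

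> For each secondary and tertiary outcome, a linear mixed model (REML) will be fitted to all available questionnaires, with time categorical (baseline, 2 weeks, 1, 2 and 3 months) and unstructured covariance, or compound symmetry with robust standard errors if that does not converge. Its overall time test replaces the ANOVA F test. The changes at 1 and 3 months from the same model will be reported with 95% confidence intervals for every outcome, whatever the time test shows. The false discovery rate adjustment applies to the time tests and to the 1-month and 3-month contrasts. A change is called significant only if its adjusted time test and its own adjusted p-value are both below 0.05.

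The contrasts belong inside the adjustment because a significant overall test, which an effect at 2 weeks alone could produce, does not protect them. The SAP states no significance level; 0.05 is the conventional choice and should be confirmed. The survey count in protocol section 1.a should be reconciled with its four listed times.

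The cost is SAP wording and some programming, with no new data. The unstructured model may not converge, the fallback protects less well against selective missingness, and bias is removed only when missingness depends on observed data.

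If the ANOVA is kept, the minimum is to run it on baseline, 1 and 3 months, and to report the 1-month and 3-month changes on all available pairs whatever it shows. That recovers most of the precision at 1 month (ratio 1.01-1.13). The ANOVA itself still rests on complete rows, and under pure dropout those are the same participants as with five occasions.
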